13.2. Reproduction Risks: N/A

13.3. Risks to Others: N/A

14. Potential Benefits to Participants

14.1. Potential Benefits:

There are likely no direct benefits to individual participants. Individuals in both groups may increase their activity level during the study period due to prompting from the device. Should the intervention be effective, participants may increase their awareness about melanoma and risk factors for a second melanoma and may decrease their own risk through improved UVR exposure protection habits.

15. Statistical Considerations

15.1. Data Analysis Plan:

All questionnaires have been previously developed and implemented and will be scored using standard methods.

15.2. Power Analysis:

Anticipating 85% of those recruited to the study complete the 12 week follow-up survey, a sample size of N=314 participants with outcome data is expected. A sample size of 314 will achieve 95% power to detect an effect size of 0.40 between intervention and control groups using a two-sided two-sample t-test assuming a significance level of 0.05. The effect size is similar to that found in an intervention to promote sun protection behaviors in high-risk individuals with the same primary outcome ¹⁹. Importantly, it will also achieve 70% power to compare report of sunburn during the intervention period between the two groups (detect 20% of the control participants reporting a sunburn – as seen in our preliminary data - and 10% of the intervention participants reporting a sunburn) as statistically significant at 0.05 significance level.

15.3. Statistical Analysis:

PROTOCOL TITLE: Wearable device intervention to improve sun behaviors in melanoma survivors

VERSION DATE: 07/19/2021

Statistical analysis will focus on evaluating the efficacy, unintended consequences and implementation of the intervention in this RCT. The main analysis of the primary outcome (self-reported overall sun protection score) will be a two-sample two-sided two-sample t-test comparing scores at the end of the intervention period (12 weeks) between intervention and control groups. Randomization should result in two groups that are similar for patient characteristics and other extraneous factors that may influence sun exposure and protection behaviors, however, we will compare the randomized groups by Wave, gender, age, stage of disease, device use (low/high), and baseline measures of sun protection and exposure behaviors using two-sample t-tests and Chi-squared tests to identify potential confounding factors which may not be balanced between the two groups. We will supplement the primary analysis with a multivariate linear regression model to account for any identified differences at baseline. A secondary analysis will explore changes in the sun protection score over the intervention period (baseline, weeks 4, 8 and 12) using a mixed effects regression model. This analysis will not be completed until both Waves have been conducted.

Secondary analyses will focus on each self-reported sun protection behavior separately, sunburns, intentional tanning, skin cancer knowledge, and physical activity and health behaviors by comparing the intervention and control participants over the study intervention period and 1 year post-completion. Analyses will be conducted using Chi-squared and t-tests as appropriate for univariate analyses at each time point and logistic and linear regression models for multivariate analyses. Daily UVR data (minutes of UVR exposure per day) will be summarized using the area under the curve (AUC) over the 12 week intervention period. Proper transformation (e.g. log-transformation) will be applied if the AUC data are skewed. The two groups' AUC will be compared using similar methods as proposed above. The association between sun exposure and its potential moderating effect on sun protection behaviors during the intervention will be investigated using linear mixed effects models including main and interaction effects, adjusting for potential confounders. To address any potential intervention effects in the control group, we will compare the baseline and post-intervention sun protection behaviors scores using paired t-tests, stratifying by randomization group. The proportions of survivors in the intervention and control groups with potentially clinically significant depression and anxiety will be compared using Chi-squared tests and supplemented with multivariate logistic regression models. Finally, descriptive statistics will be used to summarize the implementation metrics

PROTOCOL TITLE: Wearable device intervention to improve sun behaviors in

melanoma survivors

VERSION DATE: 07/19/2021

both across and within randomization group both between Waves 1 and 2 and after completion of the study.

We plan to perform all primary statistical analyses following intention-to-treat (ITT) procedures. That is, all subjects allocated to a treatment or intervention will be followed up, evaluated, and analyzed as members of that group or treatment arm regardless of their compliance with the assigned treatment. While it is not expected that participants will be incorrectly assigned, some may not use the device and certain features. For that reason, we will also summarize device use and consider sensitivity analyses exploring the intervention effect using per-protocol methods (incorporating device use) as opposed to ITT. *A priori*, we anticipate that the amount of use of the intervention will predict sun protection and exposure behaviors, though we will likely be underpowered for this analysis.

Every effort will be made to encourage participants' compliance and data completeness. Nevertheless, we expect some amount of missing data. We plan to perform a comprehensive missing data analysis employing statistical methods that are valid under different missingness assumptions to determine if conclusions are sensitive to missing data. The primary missing data method will be multiple imputation using the Markov Chain Monte Carlo (MI-MCMC) method^{36,37} assuming that data are missing at random—that is, the probability that an observation is missing can depend on the observed data but not on the missing data. We will include appropriate baseline variables into the MCMC procedure to make the conditional independent missing assumption less stringent. If the treatment group is associated with missingness, we will conduct multiple imputation for each treatment group separately³⁸. The MI-MCMC method allows arbitrary missing patterns including intermittent missing and dropout. We will also perform a simple imputation analysis as a sensitivity analysis; specifically, the linear interpolation method will be used for intermittent missing (e.g., when people forget to charge or wear the device), while the last week average value carried forward method will be used for dropouts, assuming that the average of the last 7 days' data will be a good estimate of the missing data.

15.4. Data Integrity:

Data will be entered and stored in REDCap. Data will be reviewed for completeness and cleanliness on an ongoing basis by the study coordinator and statistician.

16. Confidentiality

PROTOCOL TITLE: Wearable device intervention to improve sun behaviors in

melanoma survivors

VERSION DATE: 07/19/2021

16.1. Data Security:

All study investigators and staff will be fully trained on data safety and participant confidentiality using appropriate HealthPartners, CITI and University of Minnesota courses. An electronic copy of the signed consent and HIPAA forms will be stored on an AHC-IS supported server and the paper copy (if collected) will be stored in a locked file cabinet in a locked office. The consent form and other research information will NOT be placed in the participants' medical record.

Electronic data will be entered by the study coordinator and will be stored on the secure REDCap database. Study data will be de-identified before data analysis. Only the researchers directly involved with the study will have access to the data. Identifying data will be stored until completion of the study and manuscript submission.

17. Provisions to Monitor the Data to Ensure the Safety of Participants

17.1. Data Integrity Monitoring:

The PI will review all signed consent and HIPAA authorization forms for completeness at the time of participant entry into the study.

Apart from the UVR and physical activity data that are automatically collected by the wearable devices, data collection will occur primarily using REDCap, which will be set up to ensure data are clean and ready for analysis. Reports within REDCap will be used to identify missing data.

17.2. Data Safety Monitoring:

This study carries minimal risk and therefore the PI will assume responsibility for monitoring and reporting safety concerns/events to the University of Minnesota IRB. Events requiring prompt reporting include any adverse event that requires a change to the protocol or consent form, any unauthorized disclosure of confidential information, any unresolved subject complaint or any protocol deviation that resulting in harm or the unanticipated death of an enrolled subject.

Any event requiring prompt reporting to the IRB will also be reported to the Masonic Cancer Center's SAE Coordinator (email - [contact]).

18. Provisions to Protect the Privacy Interests of Participants

18.1. Protecting Privacy:

Identifying information will be kept private and secure as described above. Identifiers will be removed prior to data analysis. The records will be identified only with a unique ID number on an encrypted database. Data

PROTOCOL TITLE: Wearable device intervention to improve sun behaviors in melanoma survivors

VERSION DATE: 07/19/2021

transfer will only occur with de-identified data with encrypted transfer of all information containing protected health information between participants and study databases.

Participants will be reminded they do not need to answer any survey questions they do not want to and that they can withdraw from the study at any point.

18.2. Access to Participants:

All participants will be asked to provide a signed HIPAA authorization form indicating their agreement for the research study team to access their medical records pertaining to their melanoma diagnosis and treatment.

19. Compensation for Research-Related Injury

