- MI-MCMC Multiple imputation Markov Chain Monte Carlo
- QOL Quality of life
- UTAUT Unified Technology Acceptance and Use Theory
- UVR Ultraviolet radiation

PROTOCOL TITLE: Wearable device intervention to improve sun behaviors in

melanoma survivors

VERSION DATE: 07/19/2021

1. Objectives

1.1. Purpose:

Our purpose is to improve sun protection behaviors and reduce sun exposure among melanoma survivors by increasing their awareness of ultraviolet radiation (UVR) exposure by using a wearable UVR-sensor enabled technology device and corresponding mobile application designed to reduce sun exposure and promote healthy sun protection habits.

The Specific Aim of this study is to evaluate the effectiveness of a UVR-sensor wearable device intervention to improve sun protection behaviors and reduce UV exposure and sunburns in a randomized controlled trial in melanoma survivors.

2. Background

2.1. Significance of Research Question/Purpose:

Melanoma, one of the most serious types of skin cancers, has been increasing in incidence over the past 30 years. With a 5-year survival rate of 93%, there are currently over one million melanoma survivors in the United States ¹. Melanoma is considered a generally preventable cancer, with excessive UVR exposure being one of the strongest risk factors for the disease ^{2,3}. Patients diagnosed with melanoma experience high rates of recurrence and second melanomas, with an approximately 9-fold increased risk of developing another melanoma ⁴. Patients who recur or have a second melanoma diagnosis have significantly worse prognosis ^{5,6}. Importantly, UVR exposure following a melanoma diagnosis can be modified to reduce risk of a new melanoma diagnosis ⁷. Our recent study found that less than half of long-term melanoma survivors reported often or always staying in the shade or wearing a hat, and 20% reported a sunburn in the past year ⁸. Therefore, while some melanoma survivors are reporting healthy UVR exposure and protection behaviors, opportunities clearly remain to reduce future melanoma risk in the majority of melanoma survivors. Therefore, it is the purpose of this study to implement an intervention to promote healthy sun protection behaviors.

2.2. Preliminary Data:

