Our preliminary data show the need for intervention in this population and highlight our extensive experience recruiting melanoma survivors, measuring sun exposure and protection behaviors in this population, and using technology devices to change health behavior.

PROTOCOL TITLE: Wearable device intervention to improve sun behaviors in

melanoma survivors

VERSION DATE: 07/19/2021

In 2009, we completed the Skin Health Study (NIH/NCI R01), a population-based case-control study to assess use of indoor tanning, lifetime sun exposure, and use of sunscreen, statins and NSAIDs in relation to melanoma. The study included men and women, ages 25-59 at diagnosis or reference date (for controls). Cases were diagnosed with a first primary invasive melanoma between July 2004 and December 2007, identified by the Minnesota Cancer Surveillance System. Controls (individuals without melanoma) were randomly selected from the State's driver license lists. A total of 1167 cases and 1101 controls completed a questionnaire about pre-diagnosis exposure (or reference date for controls) for lifetime exposure to solar and artificial UVR, skin, eye and hair color, freckles and moles, family history of skin cancer, lifetime UVR exposure, sunburns, and sunscreen use. The study resulted in seven co-authored papers ⁹⁻¹⁵.

We transitioned from the 2009 study to a series of studies to document the long-term effects of a melanoma diagnosis and treatment on survivors and compare their quality of life (QOL) and health behaviors with population controls. First, a series of focus groups were conducted to describe the breadth of experiences among melanoma survivors, focusing on the experience at diagnosis, ongoing physical, emotional and social concerns, and behavioral changes since diagnosis ¹⁶. The focus groups included 33 men and women diagnosed with Stage I-III cutaneous melanoma.

[figure not shown]
Melanoma survivors participating in this study reported a diverse set of physical, emotional, and social concerns following diagnosis. They reported a high level of isolation and loneliness, underscoring the need to increase both awareness of melanoma and chances for melanoma survivors to interact and support each other. Almost 80% reported worrying about their melanoma reoccurring or a new cancer developing. Interestingly, while many reported increased sun protection behaviors, some reported no changes and others felt as though they did not know which changes to make.

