Based on these data, a comprehensive questionnaire to address QOL issues and health behaviors of melanoma survivors was designed and tested. Then a cross-sectional study of melanoma survivors and population controls was conducted. The goal was to collect data to evaluate the impact of melanoma on long-term survivorship focusing on quality of life ¹⁷ and sun exposure and protection behaviors ¹⁸. A total of 724 melanoma survivors and 660 controls from the parent study completed the survey. Melanoma survivors were diagnosed an average of 9.6 ± 1.0 years prior to completing the survey; the majority (85.6%) had stage I disease, 6.4% had stage II

PROTOCOL TITLE: Wearable device intervention to improve sun behaviors in

melanoma survivors

VERSION DATE: 07/19/2021

disease, 6.6% had stage III disease, and 1.4% had stage IV disease. The most common anatomic site of the tumor was the trunk (35.0%), followed by legs (26.9%), arms (26.4%), and head/neck (11.7%). Almost all (99.3%) had surgery and about one-third had lymph node dissection (34.8%).

Melanoma survivors, compared to controls, reported statistically significant but only slightly higher physical functioning and bodily pain QOL subscale scores than controls and otherwise similar QOL as measured by the remaining six SF-36 subscale scores ¹⁷. Prevalence of anxiety and depression were similar between melanoma survivors and controls.

Our data regarding sun exposure and protection behaviors indicated that long-term survivors of melanoma reported greater use of sun protection behaviors than controls ⁸. Particularly important to this application, however, was the significant subgroup of melanoma survivors (20%) who experienced sunburn in the past year, reported intentional tanning (10%), did not wear a hat (67%) or stay in the shade (52%), and spent more than two hours in the sun on weekends (75%), putting them at elevated risk for future melanomas (Figure 1).

In addition to our expertise on melanoma survivors and sun protection, we also have conducted research in using technology to change behavior. In two large-scale federally funded research studies of physical activity (R01AG023410, R01-HL072947), and one large-scale federally funded study of weight-loss maintenance (R01-CA128211), collaborator [name] employed electronic devices in the form of accelerometer-based actigraphy monitors for collection of objective measures of physical activity. He served

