6.3. Release/Sharing

Data collected in this study will not be released or shared to those outside of the research team.

7. Sharing of Results with Participants

7.1. All participants (regardless of randomization group) will be provided a summary report of their personal sun exposure during the intervention period. Study results will not be shared with the participants nor will study participation be shared with their providers. Participants will have access to their own data captured by the device via their mobile application.

8. Study Population

8.1. Inclusion Criteria:

- 18-75 years old

PROTOCOL TITLE: Wearable device intervention to improve sun behaviors in melanoma survivors

VERSION DATE: 07/19/2021

- Diagnosed with cutaneous invasive melanoma within HealthPartners system since 2010
- Able to read/write in English
- Own a smartphone
- Able to provide voluntary informed consent

8.2. Exclusion Criteria:

- Inability to provide informed consent
- Pregnancy
- Patients who have opted out of their records being used for research purposes

8.3. Screening:

To identify eligible participants, HealthPartners medical claims data will be queried to identify members diagnosed with melanoma during the recruitment eligibility period (2010-forward). HealthPartners members who have a melanoma diagnosis (2 or more codes) between 2010 and the beginning of the study recruitment period will be queried from the VDW or ADW Administrative Claims database. If additional subjects need to be identified to meet recruitment goals, then HealthPartners or Park Nicollet patients who are not HealthPartners members will be queried from EMR data in the EPIC/Clarity database. ICD9 and ICD10 Codes of 172.xx and C43.xxx respectively will be used to identify eligible members or patients. Tumor registry data within the VDW may also be utilized to identify members or patients diagnosed with melanoma. Those identified as potentially eligible will be mailed an invitation letter from HealthPartners and contacted by phone to confirm eligibility.

9. Vulnerable Populations

9.1. Vulnerable Populations:

Population / Group	Identify whether any of the following populations will be targeted, included (not necessarily targeted) or excluded from participation in the study.

PROTOCOL TITLE: Wearable device intervention to improve sun behaviors in melanoma survivors

VERSION DATE: 07/19/2021

Children	Excluded from Participation
Pregnant women/fetuses/neonates	Excluded from Participation

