10.1. Local Number of Participants to be Consented as Eligible for Recruitment (Verbal): 460

Local Number of Participants to be Consented to Full Study (Written): 390

11. Local Recruitment Methods

11.1. Recruitment Process:

Trained and experienced staff of HealthPartners Institute Center for Evaluation and Survey Research (CESR) will oversee the recruitment process. The CESR has been engaged in research both within the HealthPartners patient/member population and broader community for more than 15 years and is directed by a seasoned PhD survey methodologist and health services researcher, who oversees staff of

PROTOCOL TITLE: Wearable device intervention to improve sun behaviors in melanoma survivors

VERSION DATE: 07/19/2021

bachelors and masters-level employees with experience and training in survey, interview, chart-audit, and electronic data capture for research purposes. The CESR employs REDCap (Research Electronic Data Capture)³³ as a primary data capture and management platform.

To recruit the required sample size and ensure meaningful measures of protection sun exposure, participants will be enrolled in two cohorts (Wave 1 and 2) over two consecutive summers. Recruitment will occur in the spring with the study intervention running over the summer both years to account for seasonality.

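### The 70% power for sunburn over the 12-week intervention rests on a past-year control rate; Section 15.2 should say so and give a range

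*Combined protocol and SAP*

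**What the plan says.** Section 15.2 (Power Analysis) starts from the expected follow-up: "Anticipating 85% of those recruited to the study complete the 12 week follow-up survey", which it turns into 314 participants with outcome data. After the power for the primary outcome it adds that "it will also achieve 70% power to compare report of sunburn during the intervention period between the two groups". The inputs are in the bracket that follows: to "detect 20% of the control participants reporting a sunburn", a figure it attributes to the preliminary data, against 10% in the intervention arm, at a significance level of 0.05.

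The preliminary sunburn figure appears twice, each time with the same recall window. Section 2.1 says that "20% reported a sunburn in the past year". Section 2.2 refers to the subgroup of "melanoma survivors (20%) who experienced sunburn in the past year".

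The powered outcome has a different window. Section 3.2 lists sunburn during the intervention, Section 5.2 sets the intervention at 12 weeks, and Section 11.1 places it in summer: "with the study intervention running over the summer both years to account for seasonality". Table 2 asks for the number of sunburns over the past 4 weeks at weeks 4, 8 and 12, and over the past summer at weeks 0, 12 and 64. No item asks about the past year.

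**The concern.** A reader of Section 15.2 would take the 20% as something already observed for the outcome being powered. It was observed for a full year. The plan neither gives a rate for a 12-week or summer window nor says that the yearly rate is assumed to carry over.

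The figure carries some weight. The appendix on protocol changes gives better power for sunburn, which it treats as an important secondary outcome, as the reason for raising the sample from 248 to 368. If the sunburn comparison is null, it will be read against a stated power of 70% whose control rate belongs to another time window.

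**Working it through.** **Inputs.** Control rate 20%, intervention rate 10%, significance level 0.05 and 314 analysed come from Section 15.2. The 1:1 allocation in Section 5.2 gives 314 / 2 = 157 per arm. (368 × 0.85 = 312.8, close to the stated 314.) Section 15.3 names the Chi-squared test. Section 15.2 states two-sided testing only for the t-test; I assume it for sunburn as well.

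**Formula.** With p̄ = (p1 + p2)/2,

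SE0 = √[2·p̄(1 − p̄)/n], SE1 = √[(p1(1 − p1) + p2(1 − p2))/n], power = Φ[(|p1 − p2| − 1.96·SE0)/SE1].

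**The plan's own figure, 20 vs 10%.** p̄ = 0.15. SE0 = √(0.255/157) = 0.0403. SE1 = √(0.25/157) = 0.0399. Power = Φ[(0.10 − 0.0790)/0.0399] = Φ(0.527) = 70.1%. Exact enumeration of the uncorrected Chi-squared test gives 70.5%. The stated 70% is reproduced. One-sided testing would give 80.1%, so the two-sided assumption is the one that fits.

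**The same formula at other control rates.** The documents supply none of these; all rates other than 20% are assumptions. n = 157 per arm, two-sided 0.05.

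| Control | Intervention | Effect assumption | Power |
|---|---|---|---|
| 25% | 12.5% | risk halved | 81.3% |
| 20% | 10% | risk halved | 70.1% |
| 18% | 9% | risk halved | 64.7% |
| 15% | 7.5% | risk halved | 55.7% |
| 10% | 5% | risk halved | 39.0% |
| 18% | 8% | 10 points | 75.2% |
| 15% | 5% | 10 points | 84.3% |

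Example, 15 vs 7.5%: p̄ = 0.1125, SE0 = √(0.1997/157) = 0.0357, SE1 = √(0.1969/157) = 0.0354, power = Φ[(0.075 − 0.0699)/0.0354] = Φ(0.144) = 55.7%.

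**How far the rate might fall.** Suppose a share f of the yearly risk falls in the 12 weeks, so that the 12-week rate is 1 − 0.8^f. With risk halved, f = 0.9 gives a rate of 18.2% and power of 65%; f = 0.75 gives 15.4% and 57%; f = 0.5 gives 10.6% and 41%. If all of it falls in the window, the rate stays at 20% and power at 70%. The documents do not say what f is.

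**The enlargement.** At 85% completion, 248 × 0.85 / 2 = 105.4 per arm. Going from there to 157 per arm raises power from 53% to 70% at 20 vs 10%, and from 41% to 56% at 15 vs 7.5%.

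**The case against.** The best defence is that power is always conditional on its inputs. Section 15.2 states both rates, and the calculation is correct for them. The intervention runs in summer, when much of the year's sunburn may occur, so 20% may be nearly right. Repeated 4-week recall may also pick up burns that a single past-year question misses, which would push the rate up. Sunburn is secondary, and the enlargement raised power in both scenarios computed above, so the decision to enlarge stands. All of this is sound. It limits the size of the point but does not remove it: the text presents a past-year rate as if it were the rate for the window, without stating the assumption.

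A reader might infer more than the documents support:

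- *That the sunburn comparison has less than 70% power.* That follows only if the 12-week control rate is below 20% and the effect stays at a halving. With a fixed 10-point difference, power rises as the control rate falls.
- *That 70% holds only if the yearly rate and the halving both carry over.* This is false: 18 vs 8.5% also gives about 70%.
- *That spreading the 20% evenly over 52 weeks gives the right rate.* That yields about 5% and 21% power, but it ignores the summer timing and is an extreme lower bound.
- *That the preliminary sample was too different in age.* The preliminary sample was "ages 25-59 at diagnosis or reference date" and was surveyed on average 9.6 years later, whereas the trial's "18-75 years old" is age at eligibility. The two ranges are closer than they look, and nothing in the documents links the difference to sunburn rates.

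**Conclusion.** The point stands as a minor one. The 70% is right for its inputs, but the 20% is a past-year rate and the documents do not support it for a 12-week window. For the same population and the same question, the 12-week rate cannot exceed the rate for the year that contains it, so under a halving of risk 70% is a best case. How far below it the true power lies cannot be derived from the documents. The range from 65% down to 39% rests on assumed control rates of 18% down to 10%, and the summer timing favours the upper end. A different population or the repeated 4-week questions could move the rate in either direction. The power of the primary outcome is not affected.

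**What to change.** In Section 15.2, say that the 20% is a past-year rate assumed to apply to the 12-week summer window, and replace the single 70% with a range. Suggested text:

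> The 12-week control rate is not known. With 157 per arm, two-sided 0.05 and risk halved, power is about 81% at an assumed control rate of 25%, 70% at 20%, 65% at 18%, 56% at 15% and 39% at 10%. With a fixed 10-point difference it is about 75% at 18 vs 8% and 84% at 15 vs 5%.

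If the sponsor also names the survey item for this comparison, the past-4-week reports at weeks 4, 8 and 12 together match the intervention period. The week-12 past-summer item is then the sensitivity analysis, since it may count burns from before the device arrived.

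The week-0 survey asks about the past summer before randomisation, so its pooled rate can be reported beside the range as a guide. Wave 1 enrols at most 184, so the 95% margin at 20% is at least 1.96 × √(0.2 × 0.8/184) = 0.058, about 6 points.

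The cost is a few sentences. The stated power for an important secondary outcome becomes less definite and probably less favourable. Using the three 4-week reports needs three completed surveys, while the 314 counts only completion at week 12. Enrolment, data collection and the primary analysis do not change.
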